### 15.2.1.2 Causality

Causality is a determination of whether there is a reasonable possibility that the vaccine administration is aetiologically related to/associated with the AE.

Solicited adverse events of vaccination site reactions will be considered causally related to study treatment.

For all other adverse events, the Investigator will determine a **causal relationship** to the study vaccine. Several factors will be considered in making this assessment, including: 1) the temporal relationship of the event to the administration of the study vaccine 2) whether an alternative etiology has been identified and 3) biological plausibility.

Causality of all adverse events should be assessed by the Investigator using the following question:

***“Is there a reasonable possibility that the adverse event may have been caused by the study vaccine?”***

- YES (related): There is a reasonable possibility that the study vaccine contributed to the adverse event
- NO (not related): There is no reasonable possibility that the adverse event is causally related to the administration of the study vaccine. There are other, more likely causes and administration of the study vaccine is not suspected to have contributed to the adverse event

**Probable:** Reaction that follows a reasonable temporal sequence from administration of the IMP, or that follows a known or expected response pattern to the suspected treatment; and that could not reasonably be explained by known characteristics of the Participant’s clinical state.

**Possible:** Reaction that follows a reasonable temporal sequence from administration of the IMP, or that follows a known or expected response pattern to the suspected treatment; but that could readily have been produced by a number of other factors.

**Unlikely:** Reports not following a reasonable temporal sequence from administration of the IMP; an event, which may have been produced by the Participant’s clinical state or by other environmental factors. A more likely alternative aetiology exists.

**Not related (unrelated):** Events for which sufficient information exists to conclude that the aetiology is unrelated to the IMP.

Adverse events with a causality reported as probable or possible will be considered related to the IMP. Adverse events with missing causality assessment will be regarded as related unless further specified. All other AEs will be considered as not related to IMP.

### 15.2.2 Assessment and Outcome of Adverse Events

Each AE that occurs from first vaccination to study completion/termination will be described in the eCRF (i.e. one AE per form) using the medical diagnosis (preferred), symptom, or sign, in standard medical terminology in order to avoid the use of vague, ambiguous, or colloquial expressions. Adverse events will be evaluated by the Investigator for:

- Seriousness as defined in Section 15.1.2.
- Severity as defined in Section 15.2.1.1.
- Causal relationship to vaccine exposure as defined in Section 15.2.1.2.

For each AE, the outcome will also be documented as either:

- Recovered/Resolved
- Recovered/Resolved with sequelae
- Recovering/Resolving
- Not recovered/not resolved
- Fatal
- Unknown

If the severity rating for an ongoing AE changes before the event resolves, the AE will not be reported a second time. Instead the original AE report will be revised. For purposes of data capture the highest severity rating during the course of a single AE will be the severity rating entered on the AE CRF.

**NOTE:** *A Participant's death per se is not an event, but an outcome. The event that resulted in the Participant's death must be fully documented and reported, regardless of being considered related to treatment or not.*

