#### Booster Phase:

- Frequency and severity of solicited AEs (local and systemic reactions) within 7 days after the booster vaccination
- Frequency and severity of any unsolicited AE up to Visit 9
- Frequency and severity of any vaccine-related AE up to Visit 9
- Frequency and severity of any SAE up to Visit 10
- Frequency and severity of any AESI up to Visit 10

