## **15. ASSESSMENT OF SAFETY**

### **15.1 Definitions**

#### **15.1.1 Adverse Events**

An AE is defined as any untoward medical occurrence in a Participant administered an investigational product that does not necessarily have a causal relationship with the treatment. All new abnormalities or any exacerbation in intensity or frequency (worsening) of a pre-existing condition during or after vaccination must be documented as AEs.

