### **15.1.5 Pre-existing Diseases**

Pre-existing diseases that are present before entry into the study, that are described in the medical history, and that manifest with the same severity, frequency, or duration after vaccine exposure, will not be recorded as AEs. Furthermore, routine health checks required due to pre-existing diseases will not be recorded. However, when there is an increase in the severity of a pre-existing disease, the event must be described on the AE CRF page.

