## **15.2 Collection, Documentation and Assessment of Adverse Events**

### **15.2.1 Unsolicited Adverse Events**

Participants will be provided and trained to use an electronic diary to make notes on unsolicited AEs up to D36 (Visit 4, see Section 15.3). Additionally, the Investigator will enquire about AEs during study visits. Clinically relevant laboratory parameter changes constitute unsolicited AEs, too, unless they are considered a symptom of an underlying AE or part of a syndrome that is reported as AE (e.g. presence of blood cells in urine in a person diagnosed

with urinary tract infection). In addition, symptoms noted during the symptom-driven physical exams (unless already covered by an AE) constitute AEs.

All unsolicited AEs need to be documented in the respective AE section of the eCRF during the applicable study visit (Visits 1 to 6 or unscheduled visit(s), if applicable), regardless of their source (AEs noted in the Participant diary [see Section 15.3], open question to Participant, laboratory parameters, symptom-driven physical examination). Serious adverse events will continue to be documented until the end of the study.

Any symptom is regarded as a separate AE. However, if the Investigator considers several symptoms to be in the context of one underlying diagnosis, the Investigator may merge these symptoms into one single appropriate AE. The AE term entered into the eCRF should contain all symptoms summarized to one event (e.g. 'Influenza with flu-like-symptoms, fever and headache').

The Investigator will follow-up each AE until it is resolved or until the medical condition of the Participant is stable. All relevant follow-up information will be reported to the Sponsor until the end of the study for each Participant. Serious adverse events ongoing at the time of Visit 8 will be followed until resolution or achievement of stable clinical conditions, latest until the overall end of the study.

**Beyond study end, SAEs that are fatal, life-threatening or suspected to be related to study treatment will be followed up to be reported until 6 months after the last study visit of the respective Participant.**

The following information will be documented for each AE: severity, causality, outcome, and seriousness, medically-attended, action taken to treat AE, action taken on IMP, start and stop dates.

Booster Phase:

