- Participant with any serious unsolicited AE up to Visit 10 in the booster phase
- Participant with any AESI up to Visit 10 in the booster phase

In addition, following summaries will be presented by SOC and PT for the booster phase:

- Summary of unsolicited AEs up to Visit 9 in the booster phase
- Summary of treatment related unsolicited AEs up to Visit 9 in the booster phase
- Summary of serious unsolicited AEs up to Visit 9 in the booster phase
- Summary of AESI up to Visit 9 in the booster phase
- Summary of unsolicited AEs up to Visit 10 in the booster phase
- Summary of treatment related unsolicited AEs up to Visit 10 in the booster phase
- Summary of serious unsolicited AEs up to Visit 10 in the booster phase
- Summary of AESI up to Visit 10 in the booster phase
- Summary of unsolicited AEs by maximum severity up to Visit 9 in the booster phase

- Summary of unsolicited AEs by closest causality relationship up to Visit 9 in the booster phase
- Summary of unsolicited AEs by maximum severity up to Visit 10 in the booster phase
- Summary of unsolicited AEs by closest causality relationship up to Visit 10 in the booster phase

Adverse events that started in the booster phase will be presented separately in participant data listings.

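### An unsolicited AE ongoing at the booster that then worsens can carry its post-booster grade into the Day 208 severity table and be missing from the booster-phase listing

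*Protocol*

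**What the plan says.** **Recording rule.** Protocol 15.2.2 covers an ongoing AE whose grade changes: "If the severity rating for an ongoing AE changes before the event resolves, the AE will not be reported a second time". It continues: "Instead the original AE report will be revised", and "the highest severity rating during the course of a single AE will be the severity rating entered on the AE CRF". It does not say what happens to the start date, and it does not mention a change in seriousness.

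**Data captured.** Protocol 15.2.1 lists the items held for each unsolicited AE: "severity, causality, outcome, and seriousness, medically-attended, action taken to treat AE, action taken on IMP, start and stop dates". A date of grade change is not among them.

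**Assignment to the booster phase.** SAP 7.2.1 says: "Adverse events that started in the booster phase will be presented separately in participant data listings". That sentence concerns listings. The booster summary tables are described only as running up to Visit 9 or Visit 10 in the booster phase, with no rule on onset.

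**Grade shown.** SAP 7.2.1 summarises each participant at the most severe grade. Table 14.2.1.15 gives maximum severity to Day 208. The SAP index marks it No for Part A, No for the second interim and Yes for the third, and SAP section 10 places the third interim after Visit 9.

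**Endpoints affected.** Among the booster-phase safety endpoints in Protocol 10.3.1.2 is "Frequency and severity of any unsolicited AE up to Visit 9".

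**Neighbouring definitions.** Protocol 15.1.1 requires that "any exacerbation in intensity or frequency (worsening) of a pre-existing condition during or after vaccination must be documented as AEs". Protocol 15.1.5 says that diseases present before study entry which "manifest with the same severity, frequency, or duration after vaccine exposure, will not be recorded as AEs".

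**The concern.** Part C exists to describe what follows a third dose. One way a dose can do harm is to aggravate something already present. Under the recording rule, aggravation of an AE that is already on file updates the old record instead of creating a new one. With one start date and one grade per record, a grade reached after the booster is tied to an onset that lies in the primary-series window.

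Two summaries could then mislead in opposite directions. The primary-series severity table to Day 208 would show a grade that was not reached by Day 208. The booster-phase output would omit an event that occurred after the booster. A reader of the third interim would have no sign in either place that this had happened.

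**Working it through.** The documents give no count or rate for such events, so there is no figure of the plan to reproduce. The check has three parts.

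**1. Trace one event through the rules.** The dates are assumed. The booster is placed on Day 265, about eight months after the second dose (22 + 243 = 265). Visit 9 is then Day 265 + 28 = 293. The AE starts on Day 150 at Grade 1, is ongoing at the booster, and reaches Grade 3 on Day 267. Windows are applied by start date.

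| How it is recorded | Day 208 table (start ≤ 208) | Booster phase (265 ≤ start ≤ 293) |
|---|---|---|
| One revised record: start 150, Grade 3 | Grade 3 | No event |
| Two records: start 150, Grade 1; start 267, Grade 3 | Grade 1 | Grade 3 |

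The first row is what 15.2.2 gives if the start date is kept. If the single record's start date were instead reset to Day 267, the booster phase would show Grade 3, but the Part B event would drop out of the Day 208 table (267 > 208). One record with one start date cannot serve both windows.

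The timing of the output matters. A Day 208 table cut before the booster could not contain a post-booster grade. Protocol 16.5 does mention a Part B analysis after Visit 6, but SAP section 10 and the output index make no separate provision for it. The first run they schedule comes after Visit 9.

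**2. Size of one affected participant.** Protocol 16.1 and SAP 2.5 expect up to about 80 boosted participants.

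- One participant: 1/80 = 1.25%.
- Clopper-Pearson upper limit for 0/80: 1 − 0.025^(1/80) = 4.5%.
- Clopper-Pearson limits for 1/80: lower 1 − 0.975^(1/80) = 0.03%; upper, the 0.975 quantile of Beta(2, 79), 6.8%.

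A participant whose only booster-phase event in a category is such a worsening therefore moves that rate from 1.25% (95% CI 0.03 to 6.8%) to 0% (0 to 4.5%). If 0 to 4 participants were affected, which is an assumption, the shift would be 0 to 5.0 points (4/80 = 5.0%).

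**3. Set the definitions side by side.** Protocol 15.1.1 makes worsening of a pre-existing condition an AE, and 15.6 says much the same for examination findings. Protocol 15.1.5 describes pre-existing disease as present before study entry. An AE that began in Part A or B did not exist at entry, so it does not clearly qualify, and 15.2.2 is the only rule that plainly applies to it.

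There is a separate mismatch. The exemption in 15.1.5 joins severity, frequency and duration with *or*. Read literally, unchanged severity is enough even when frequency rises, and the section's last sentence requires recording only for increased severity. Protocol 15.1.1 requires it for frequency as well.

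**The case against.** The case on the other side is substantial, and most of it limits the point without removing it.

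- **Onset is inferred.** Protocol 15.2.2 does not say that the start date is kept. That is correct, and the conclusion is conditional on it. Keeping the date is the natural meaning of revising an existing report.
- **Few participants can be affected.** Protocol 11.6 withdraws from further vaccination anyone with an SAE or AESI considered possibly or probably related. It does the same for certain Grade 3 unsolicited AEs that are related or unresolved. Booster entry requires general health and excludes acute illness, although stable disease is allowed. What remains is mainly stable or unrelated ongoing AEs. This stands.
- **Other data exist.** e-Diary notes on unsolicited AEs run to Visit 10, Grade 3 diary entries prompt a call, and safety laboratory tests are repeated at Visits 7, 8 and 9. A reader might infer that the misassignment could never be repaired at analysis. The documents do not support that: these sources could date some worsenings, even though the specified AE record does not.
- **One record at the highest grade is a legitimate capture choice.** It is, but it was written for an event followed through to resolution. It does not fit an event that spans two separately reported vaccination phases.

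Three stronger readings are tempting and should not be drawn:

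- **Seriousness is back-dated by rule.** Protocol 15.2.2 speaks of severity only. SAEs and AESIs have their own 24-hour route (Protocol 15.11.1). Seriousness would move only if the same record happened to be revised, or where a Grade 4 event is reported as an SAE under 15.1.2.
- **Day 36 severity is inflated.** The SAP index contains no table of unsolicited AEs by severity to Day 36.
- **The booster tables exclude these events.** Selection by start is stated for listings. For the tables the SAP is silent, so exclusion is likely but not specified.

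**Conclusion.** The point holds in a limited form. For an unsolicited AE that begins in Part A or B, is ongoing at Visit 7 and worsens in grade after the booster, the stated rules produce one record at the post-booster grade with no date of worsening. If the start date is kept, that grade appears in Table 14.2.1.15 and the event is absent from the booster-phase listing. Whether it enters the booster summary tables is not defined.

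Each affected participant is worth up to 1.25 percentage points at 80 boosted. The number affected is not given and is probably small. Solicited reactions have their own seven-day post-booster window and are outside the problem, and real-time SAE reporting is not weakened. The harm is confined to how windowed summaries attribute grade and onset. The change is still worth making because the repair is cheap and the booster endpoints concern both frequency and severity.

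The mismatch between 15.1.1 and 15.1.5 over frequency stands independently of the booster question.

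**What to change.** 1. **Protocol 15.2.2 and eCRF instructions.** For an AE ongoing at a vaccination visit that worsens after that vaccination, either record the date of worsening, or close the record at its pre-vaccination grade and open a new one dated at the worsening. State which date then counts as onset.
2. **SAP 7.2.1.** Define a booster-phase AE, for tables and listings alike, as one that starts, worsens in grade or becomes serious after the Visit 7 vaccination.
3. **SAP windowed tables.** Cap the grade shown at the highest reached by the end of the window, so that the Day 208 table does not carry later grades.
4. **Protocol 15.1.5.** Reconcile the exemption and its last sentence with 15.1.1, so that worsening in frequency is recorded. State also whether an AE ongoing at Visit 7 counts as pre-existing for the booster.

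The cost is some protocol and eCRF wording, one date field or an additional record, and a short SAP rule. The downside is a few more AE records and the possibility that one illness appears in two windows, which a table footnote can explain.

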### 15.2.3 Solicited Adverse Events

Solicited AEs will be collected in the e-Diary by the Participant for 7 consecutive days after each vaccination, starting on the day of vaccination. They will be graded by the investigator

or the designee according to the FDA's Toxicity Grading Scale for Healthy Adult and Adolescent Volunteers Enrolled in Preventive Vaccine Clinical Trials, see Table 4, Table 5 and Table 6.

For solicited AEs which are serious and/or medically attended, the investigator carries out more detailed assessments are performed for unsolicited AEs (causality, outcome, action taken) and documents them in the eCRF. For solicited local and systemic AEs persisting beyond 6 days after vaccination, stop date is also documented in the eCRF (AE section).

### 15.2.3.1 Injection Site Reaction – Measurement and Evaluation

Solicited injection site reactions include injection site pain, itching, tenderness, redness and swelling/induration. Participants will be provided with a measuring tool to measure the size of any measurable injection site reaction (longest diameter).

**Table 4 Grading of Injection Site Reactions**

Vaccine-specific Criteria	Mild (Grade 1)	Moderate (Grade 2)	Severe (Grade 3)	Potentially Life Threatening (Grade 4) c
Pain	Does not interfere with activity	Repeated use of non-narcotic pain reliever > 24 hours or interferes with activity	Any use of narcotic pain reliever or prevents daily activity	Emergency room visit or hospitalisation
Tenderness	Mild discomfort to touch	Discomfort with movement	Significant discomfort at rest	Emergency room visit or hospitalisation
Erythema Redness a	2.5–5.0 cm 0.98–1.96 inch	5.1–10.0 cm 1.97–3.94 inch	> 10.0 cm > 3.94 inch	Necrosis or exfoliative dermatitis
Induration Swelling b	2.5–5.0 cm (0.98–1.96 inch) and does not interfere with activity	5.1–10.0 cm (1.97–3.94 inch) or interferes with activity	> 10.0 cm (> 3.94 inch) or prevents daily activity	Necrosis

a In addition to grading the measured local reactions at the greatest single diameter.

b Induration/swelling should be evaluated and graded using the functional scale as well as the actual measurement.

c Any Grade 4 injection site reaction will be reported as SAE, Grade 3 severity should be documented.

### 15.2.3.2 Systemic Reactions – Measurement and Evaluation

Solicited systemic reactions include fever/body temperature (Section 15.2.3.3), fatigue, headache, nausea/vomiting, muscle pain.

**Table 5 Grading of Systemic Reactions**

Vaccine-specific Criteria	Mild (Grade 1)	Moderate (Grade 2)	Severe (Grade 3)	Potentially Life Threatening (Grade 4) d
Nausea/vomiting	No interference with activity or one to two episodes/24 hours	Some interference with activity or > 2 episodes/24 hours	Prevents daily activity, requires outpatient IV hydration	Emergency room visit or hospitalisation for hypotensive shock
Headache	No interference with activity	Repeated use of non-narcotic pain reliever > 24 hours or some interference with activity	Significant; any use of narcotic pain reliever or prevents daily activity	Emergency room visit or hospitalisation
Fatigue	No interference with activity	Some interference with activity	Significant; prevents daily activity	Emergency room visit or hospitalisation
Myalgia	No interference with activity	Some interference with activity	Significant; prevents daily activity	Emergency room visit or hospitalisation

a Any Grade 4 systemic reaction will be reported as SAE, Grade 3 severity should be documented.

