## 10.3 Study Endpoints

### 10.3.1 Safety Endpoint

#### 10.3.1.1 Primary Endpoint

- Frequency and severity of solicited AEs (local and systemic reactions) within 7 days after any vaccination of the primary vaccination series.

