#### 10.6.1 During staggered dose escalation period:

- **One or more Participants** experience an SAE or AESI with no likelier alternative cause than the study vaccine (i.e. related).
- **One or more Participants** experience a severe systemic allergic reaction, e.g. generalized urticaria or anaphylaxis within 24 hours following vaccine administration, with no likelier alternative cause than the study vaccine.
- **One or more Participants** experience Grade 4 local reaction at the vaccination site, characterized by ulceration, necrosis or any Grade 4 local reaction that requires emergency medical care within seven days after study vaccine administration.
- **One or more Participants** in the same treatment group experience the same Grade 3 solicited local AE 48 hours following vaccination.
- **One or more Participants** in the same treatment group experience the same severe (Grade 3 or Grade 4) solicited systemic AE within 48 hours following vaccination, with no likelier alternative cause than the study vaccine.

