**Table 6 Grading of Fever**

Mild	38.0°C – 38.4°C
Moderate	38.5°C – 38.9°C
Severe	39.0°C – 40.0°C
Potentially Life-Threatening	>40.0°C

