7.1 ANALYSIS OF PRIMARY SAFETY ENDPOINT

7.1.1 Solicited Adverse Events within 7 days after vaccination

Solicited AEs will be collected in the eDiary by the participant for 7 consecutive days after each vaccination, starting on the day of vaccination. Solicited AEs will be graded by the investigator according to the FDA's Toxicity Grading Scale for Healthy Adult and Adolescent Volunteers Enrolled in Preventive Vaccine Clinical Trials. The following solicited reactions will be assessed:

Solicited injection site reactions: These include injection site pain, itching, tenderness, redness and swelling/induration.

Solicited systemic reactions: These include fever/body temperature, fatigue, headache, nausea/vomiting, muscle pain.

All fever measurements should be recorded by the participant in the participant diary including the first value that shows a return to normal body temperature. Oral body temperature $\geq 38.0^{\circ}\text{C}$ is defined as fever. If more than one body temperature value is recorded in the participant diary on a given day, the highest daily temperature reading will be recorded in the eCRF.

The number and percentage of participants with solicited injection site and systemic AEs within 7 days after vaccination along with the exact 95% Clopper-Pearson confidence interval (CI) for all AE rates will be presented for each dose group and overall. Differences between the dose groups will be assessed for significance using Fisher-Freeman-Halton exact test and p-values will be presented for this test. If the overall group difference is statistically significant then multiplicity adjusted p-values (using Hochberg method) for pairwise group differences will be calculated for Fisher's exact test.

Solicited AEs will also be summarized by severity grades. If a participant has the same reaction with multiple severity grades then the most severe grade will be counted.

All data for solicited adverse events will also be presented in participant data listings.

Booster Phase:

The number and percentage of participants with solicited injection site and systemic AEs within 7 days after booster vaccination along with the exact 95% Clopper-Pearson confidence interval (CI) for all AE rates will be presented. Solicited AEs will also be summarized by severity grades. If a participant has the same reaction with multiple severity grades then the most severe grade will be counted.

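### Tables 4 and 5 have sites document Grade 4 solicited reactions as Grade 3, so the maximum-severity tables cannot show Grade 4 for eight non-fever reactions

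*Protocol*

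**What the plan says.** The primary safety endpoint in Protocol 10.3.1.1 is "Frequency and severity of solicited AEs (local and systemic reactions) within 7 days after any vaccination of the primary vaccination series". Severity is therefore part of the endpoint.

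Protocol 15.2.3 refers to Tables 4, 5 and 6 for grading. Each has a fourth, potentially life-threatening level. SAP 7.1.1 adopts the same scale: "Solicited AEs will be graded by the investigator according to the FDA's Toxicity Grading Scale for Healthy Adult and Adolescent Volunteers". For the severity summary it adds: "If a participant has the same reaction with multiple severity grades then the most severe grade will be counted".

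Two footnotes then change what is written down. For injection site reactions, Table 4 says: "Any Grade 4 injection site reaction will be reported as SAE, Grade 3 severity should be documented". For systemic reactions, Table 5 says: "Any Grade 4 systemic reaction will be reported as SAE, Grade 3 severity should be documented". Table 6 keeps a top category for fever above 40.0°C, labelled "Potentially Life-Threatening", and has no such footnote.

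Elsewhere the protocol treats Grade 4 as a grade that gets assigned. Section 15.1.2 requires events graded 4 to be reported as SAEs and points to 15.2.3 for solicited events. Section 10.6.2 has Grade 3 and Grade 4 solicited events confirmed with the site before the study is stopped.

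**The concern.** In Table 5 a headache that stops normal activity is Grade 3, and one that leads to an emergency-room visit or admission is Grade 4. Under the footnote both are documented as Grade 3. The severity tables would then report no Grade 4 headaches whatever happened, and a reader could not tell a true zero from an imposed one. The same holds for the other reactions in Tables 4 and 5. In a first-in-human study, the top grade of the primary safety endpoint would be hidden in the tables meant to show it.

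**Working it through.** No plan figure is at issue, so the check sets the passages side by side.

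1. **Reactions affected.** Table 4 grades pain, tenderness, redness and swelling/induration (4). Table 5 grades nausea/vomiting, headache, fatigue and myalgia (4). 4 + 4 = 8 reactions have a Grade 4 definition and a footnote that replaces it. Two other solicited reactions stand apart. Fever has Table 6, and 15.2.3.3 sends the highest daily temperature to the eCRF, so its grade can be recovered. Itching is solicited but has no row in Table 4.

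2. **Effect on the tables.** For any of the eight reactions in any group, let g3 and g4 be the numbers of participants whose true maximum grade is 3 or 4. Following the footnotes, the documented counts are Grade 3 = g3 + g4 and Grade 4 = 0. The SAP rule of counting the most severe grade chooses among recorded grades, so it cannot restore g4. This applies to SAP Tables 14.2.1.4 and 14.2.1.5 (primary series) and 14.2.1.26 and 14.2.1.27 (booster).

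3. **Is the merging declared?** SAP 7.1.1 has no rule that collapses Grade 4 into Grade 3. SAP 13.1 lists one change from the protocol, which concerns stratification by serostatus.

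4. **Is the event shown elsewhere?** It is reported as an SAE, and it can appear in Listings 16.2.1.1 and 16.2.1.1.1 (solicited AEs from the AE eCRF). But the serious-event summaries itemised in SAP 7.2.1, and Tables 14.2.1.9, 14.2.1.10, 14.2.1.19, 14.2.1.33 and 14.2.1.37, are all for serious unsolicited AEs. The endpoints in Protocol 10.3.1.2 cover any SAE, which is wider. Table 14.2.1.1 is an overall AE summary, but the SAP does not say that it counts serious solicited events. No itemised summary table is therefore specified to show a Grade 4 solicited reaction as such.

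5. **Size in Part A.** Protocol 8.5.1 reports severe solicited AEs in two participants (headache and fatigue). If severe there means documented as Grade 3, at most 2 of the planned 150 participants, 2/150 = 1.3%, could have a Grade 4 event recorded as Grade 3. Nothing in the documents suggests that either was Grade 4.

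**The case against.** The best defence is that the footnotes are part of the scale the protocol adopts. Section 15.2.2 evaluates severity under 15.2.1.1, which stops at Severe (Grade 3). On that reading the severity field is capped at 3 and the SAE report carries the rest. This stands in part. Section 15.2.2 says "the highest severity rating during the course of a single AE will be the severity rating entered on the AE CRF", and a reader might see a direct contradiction there. On a three-level field, however, the highest possible entry is Grade 3, so that conflict is weak and I do not rely on it. The defence does not explain why 15.1.2 and 10.6.2 speak of solicited events graded 4, why Table 6 has no such note, or why the SAP names the FDA scale without mentioning a cap.

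A reader might also infer that the stopping rules are disabled. The documents do not support that. The sentinel systemic criterion in 10.6.1 applies when participants "experience the same severe (Grade 3 or Grade 4) solicited systemic AE within 48 hours following vaccination", so recording 3 instead of 4 changes nothing. The sentinel local criterion names Grade 4, but it also describes the event clinically. A Grade 4 local reaction is reported as an SAE, and 15.2.1.2 always counts solicited site reactions as related, so it meets the separate related-SAE criterion. The footnote on Grade 4 events in 10.6.2 relies on the same route.

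A third inference is that the choice of dose was distorted. Protocol 8.5 says the high dose was already selected after Day 36, and the bound of two participants leaves little room for an effect. Booster recipients all get one dose level, and the SAP plans no dose-group test of their solicited events.

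**Conclusion.** The point holds as a defect in severity recording and tabulation. Followed as written, the footnotes set the Grade 4 count to zero for eight reactions in four severity tables, in conflict with the passages cited above, and no itemised serious-event summary makes up for it. The likely numerical effect is small in Part A, at most two participants, and unknown for the booster, where up to about 80 are expected. The documents do not support a claim that stopping rules fail or that the dose choice was wrong.

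This rests on three assumptions. The footnotes refer to the severity field that feeds the tables; the eCRF and table shells are not in the documents. Sites follow the footnotes. Fever is outside them: 15.2.3.2 lists fever as a systemic reaction, so the Table 5 wording could be read to cover it, but the recorded temperature allows the grade to be recovered.

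**What to change.** - Reconcile the footnotes to Tables 4 and 5 with Protocol 15.1.2, 15.2.3, 10.6.2 and Table 6 and with SAP 7.1.1, so that the observed grade (1 to 4) is documented and the SAE report is made in addition.
- Check every solicited reaction already entered as Grade 3 against the SAE forms, and correct the grade where the Table 4 or 5 definition of Grade 4 was met. Apply the same check to all dose groups.
- State in SAP 7.1.1 that Grade 4 is tabulated in Tables 14.2.1.4, 14.2.1.5, 14.2.1.26 and 14.2.1.27.
- Include serious solicited AEs in the SAE summaries, so that they match the any-SAE endpoints.

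The cost is two footnotes, an eCRF completion note, a few SAP lines and a short data check. If the eCRF severity field has only three levels, as 15.2.1.1 suggests, a fourth level must be added, which is a database change. No new data need to be collected from participants.
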